(3) Is the *improvised dressing* culturally acceptable to health care providers, patients, and families for managing SCLUs in Jamaica?

The expected study outcome is improvised dressing superior effectiveness and quality of life, when compared with usual practice, without increased safety and acceptability issues.^{13,59,60,62} The improvised dressing is likely to be the least expensive choice, with the added benefit of being available as first aid treatment throughout Jamaica. The advanced dressing is likely to be more expensive with respect to materials costs, although fewer dressing changes are anticipated and pain medication expenses are likely to be reduced. Based upon the review of the literature, no serious infections or other safety issues are anticipated for any group. However, to ensure that complications are not overlooked, in addition to the onsite researchers' vigilance, weekly wound photos will be assessed for complications (signs of infection, wound deterioration, or clinically relevant maceration) by two off-site blinded wound experts, Drs. [name] and [name].

Definitions:

Sickle cell leg ulcer – a wound in a HbSS or HbS β^0 positive patient, open greater than one month,⁷ below the level of the knee excluding the plantar surface of the foot.

Closed wound -100% epithelialized with no discernible scab or exudate production (paper napkin remains dry when lightly pressed against area, and no recurrence in the subsequent two weeks)

Safe – infection and other complications (healing-impairing maceration, keloid, and contracture rates) not statistically significantly higher than usual practice, with no major adverse events attributable to the method

Effective – ulcer closure rates or ulcer surface area reduction rates not statistically significantly lower than usual practice

Acceptable – average acceptability scores of 4 or higher on a 1-5 scale

3. Methods and Materials

a. Study design

This study will be a targeted-blinded (the off-site wound experts and the local physicians verifying wound closure and/or complications will be blinded to the randomization group), randomized controlled trial with three arms: (1) usual practice (negative control), (2) the improvised dressing, and (3) the advanced dressing (positive control). The expected outcome is improvised and advanced dressing superiority.

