Although non-inferiority is an acceptable outcome for the improvised dressing, the review of the literature supports the expectation that it will outperform usual practice. This superiority study design eliminate the motive for the blinded evaluators to minimize differences between groups, biasing the results.¹³ If superiority is attained, the results will be evaluated with intent to treat (ITT) analysis.

If superiority is not demonstrated, the data for the improvised dressing and usual practice dressing will be re-evaluated to assess for noninferiority.¹³ Contrary to superiority trials where use of intention-to-treat is employed to protect against type 1 error, the appropriate approach for noninferiority trials is to use a per-protocol approach,¹³ which, at worst, would exaggerate the differences between treatment groups, thereby yielding a more conservative estimate in the setting of a noninferiority trial.¹³ Thus, only those patients completing treatment in the group to which they were randomized will be retained for any non-inferiority analyses (see appendix for further details).

b. Study population

Individuals diagnosed with sickle cell disease who have a SCLU and reside in the parishes of St. Catherine, St. Andrew, or Kingston parishes of Jamaica and respond to advertisements, recruitment phone calls, or flyers posted at the Sickle Cell Unit (SCU) clinic and UHWI prior to and during the enrollment period will be invited to participate in the study. Members of the UHWI surgical team will call all patients identified by the SCU as having had a SCLU within the past two years to invite them to participate in the study. Jamaican residents who otherwise qualify but who live outside the study area will be included only if they agree to provide their own transportation and faithfully attend all clinic visits.

c. Sample

Study participants must have HbSS or HbS β^0 sickle cell disease, be between the ages of 13 and 70, and have a chronic SCLU, defined as a wound in a patient with sickle cell disease that has been open for at least one month and is below the knee, excluding the plantar surface of the foot. All SCLUs on a single patient will be dressed with the same dressing protocol. The largest ulcer at initial presentation is the study SCLU. If two or more SCLUs in close proximity join into

an enlarged ulcer during the first four weeks of the study, the sum of the initial areas will be considered the initial wound size for calculation purposes.

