As a token of appreciation from the research team and an incentive for patients to return for their study clinic visits, each participant will be presented with a 500JM phone card at the end of each of the three 4-week study periods.

All wound management supplies for all three groups will be donated. Shipping and handling fees will be paid by the Principal Investigator with funds from a Wound Healing Foundation grant. Tallies of supplies used at dressing changes will be priced using the cost of medical supplies purchased by the SCU to determine the estimated cost of the treatment supplies for each patient. The PMD rolls will be valued at \$26.99US.⁹⁸

The Principal Investigator will de-identify the data and compile it from the patient Data Collection Tools onto an Excel spreadsheet. This spreadsheet and the de-identified wound photographs will be backed up onto the Principal Investigator's second password protected hard drive via a secure internet connection at least weekly. Two encrypted USB drives containing the data, including wound photographs, will be updated weekly on an alternating schedule and stored in a securely locked file in [name] office in UWI Department of Surgery.

i. Statistical analysis

A consultant, [name], PhD, Senior Biostatistician at The University of Texas Medical Branch in Galveston, will undertake the analysis.

When all of the patients have completed the study, the remainder of the data from the deidentified Data Collection Tools will be transcribed into an Excel spreadsheet by the Principal Investigator. The data will then be evaluated by the biostatistician using the most recent version of SPSS. Groups will be compared with respect to each of the 14 dependent variables, taking into account any confounding from the 11 independent variables. Results will be reported using descriptive statistics (means, modes, medians, frequencies), student's t test, and ANOVA with 95% CIs, using intent-to-treat.¹³ If the improvised dressing does not attain statistical superiority to usual practice, 80% CIs will be calculated with drop-outs removed from the analyses to evaluate noninferiority.^{13, Appendix: From Oczkowski SJW} Complications will be evaluated both individually and collectively by collapsing the pertinent columns.

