Research questions (1) and (2) will be addressed by using analyses of covariance (ANCOVA) to determine if patients in the improvised dressing group (Group 2) had superior results (95% CI's will fall within *f*, the superiority margins) from usual practice (Group 1) or advanced dressings (Group 3), or, if this is not demonstrated, failed to vary significantly (80% CI's will fall within *f*, the inferiority margins) from usual practice (group 1) or advanced dressings (group 3) with respect to each of the dependent variables, controlling for relevant patient characteristics (the independent variables).

Research question (3) will be addressed with descriptive statistics across Likert items regarding endorsement of and concerns with use of the improvised dressing clinically or in future studies. Qualitative comments will be summarized across providers into content themes. Any differences between nurses, patients, family members, and physicians will also be explored and noted.

All health care providers at UHWI participating in the study will be surveyed to explore their concerns as well as their opinions about each dressing choice, using both qualitative open-ended and a quantitative question on a Likert scale. Results will then be shared with the participating clinical staff to provide them with the evidence concerning each of the three dressing protocols.

j. Data handling and record keeping

All study data will be transferred from written documents to the Principal Investigator's password protected electronic devices, de-identified, and then transmitted over secure internet connections to the backup hard drive in the USA. The paper study documentation and the two encrypted USB drives containing the raw data will be stored in a securely locked file in in [name] office in UWI Department of Surgery for a period of at least two years after the study has been published, after which they may be destroyed.

When all of the patients have completed the study, members of the UHWI research team will proofread the Excel spreadsheet with the de-identified data for transcription errors. This data will then be evaluated by the biostatistician using the most recent version of SPSS.

4. Ethical Considerations

This study will be approved by the Ethics Review Committee (ERC) at UWI and the Jamaican Ministry of Health (MOH) prior to its implementation. It will be listed on clinicaltrials.gov prior to the recruitment of the first study patient.

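### Read literally, the superiority and noninferiority rules for questions 1 and 2 are containment (equivalence) rules, and the sections disagree on which comparator noninferiority covers

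*Combined protocol and SAP*

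**What the plan says.** Four places in the document bear on the decision.

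- **Section 3i, paragraph on questions 1 and 2.** By ANCOVA, group 2 is judged to have "had superior results (95% CI's will fall within" f, the superiority margins. Failing that, it is judged to have "failed to vary significantly (80% CI's will fall within" f, now called "the inferiority margins) from usual practice (group 1) or advanced dressings (group 3) with respect to each of the dependent variables". Both rules name group 1 or group 3.
- **Section 3i, preceding paragraph.** Groups are compared with 95% CIs under intention to treat. Then: "If the improvised dressing does not attain statistical superiority to usual practice, 80% CIs will be calculated with drop-outs removed from the analyses" to assess noninferiority. Only usual practice is named.
- **Section 3a.** Superiority of the improvised and advanced dressings is the expected outcome. If it is not shown, "the data for the improvised dressing and usual practice dressing will be re-evaluated to assess for noninferiority". Group 3 is not mentioned, and the reader is sent to an appendix for details.
- **Section 2.** Question 1 asks about usual practice and the advanced dressing; question 2 asks about usual practice only. The definition of effective is "ulcer closure rates or ulcer surface area reduction rates not statistically significantly lower than usual practice", with no margin and no reference to group 3.

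The text supplied gives f no value, scale or direction.

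**The concern.** A superiority claim needs the CI to lie wholly on the favourable side of zero, or beyond a superiority margin. A CI contained within margins shows that two treatments are similar. A rule that calls containment superiority rewards a null result and rejects a large benefit.

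The fallback has the same fault. Noninferiority restricts only the unfavourable bound, whereas containment restricts both, so a clearly better dressing can fail it. And because both rules use f, on the same data any result that meets the 95% rule also meets the 80% rule. Only the interval width, and the change of analysis set, then separates a finding of superiority from a finding of no important difference.

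The comparator is also unsettled. One paragraph of 3i lets the noninferiority rule apply against usual practice or the advanced dressing; the paragraph before it and section 3a allow usual practice only.

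The rule is to be applied to each dependent variable by an outside consultant. That analyst must either follow wording that works against the stated aim or substitute another rule, possibly after the data are in.

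**Working it through.** **Sample size input.** Section 3f gives 90 participants, about 30 per group, and up to 120 recruited for 25% dropout. Check: 90 / (1 − 0.25) = 120, which reproduces the plan's figure. The 30 per group cannot be re-derived, because no effect size, SD, power or margin is stated.

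**Assumptions.** Two-arm difference in SD units, 30 per arm, normal outcome, no covariate gain. f is read as the band from −f to +f. Its value is assumed.

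**Interval widths.** SE = √(2/30) = 0.258 SD. With t on 58 df, the 95% half-width is 2.002 × 0.258 = 0.517 SD and the 80% half-width is 1.296 × 0.258 = 0.335 SD.

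**Literal superiority rule, f = 0.8 SD.** The 95% CI lies inside ±0.8 when the estimate is within ±(0.8 − 0.517) = ±0.283.

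- True difference 0: P(|Z| < 0.283/0.258 = 1.10) = 0.73.
- True benefit 0.74: Φ((0.283 − 0.74)/0.258) = Φ(−1.77) = 0.04; the other tail is negligible.

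**Ordinary rule (95% CI above zero).** The estimate must exceed 0.517.

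- True difference 0: Φ(−2.00) = 0.023.
- True benefit 0.74: Φ((0.74 − 0.517)/0.258) = Φ(0.86) = 0.81.

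These four lines hold the half-width at its nominal value. Simulating the sample SD as well gives:

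| Rule | True difference 0 | True benefit 0.74 SD |
|---|---|---|
| Literal, f = 0.8 SD | 72% | 4% |
| Literal, f = 1.0 SD | 94% | 17% |
| Ordinary, CI above zero | 2.5% | 80% |

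With f = 1.0 SD the literal rule also passes about 48% of the time when the dressing is truly 0.5 SD worse.

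**Small f.** At f = 0.5 SD the nominal half-width of 0.517 exceeds the margin. The sample SD varies, however: the half-width falls below 0.50 SD in about 39% of trials, and the literal rule passes about 4% of the time at no effect. It is rarely met, but not impossible to meet.

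**Literal fallback, f = 0.8 SD, true benefit 0.74.** The 80% CI lies inside ±0.8 when the estimate is within ±(0.8 − 0.335) = ±0.465, with probability Φ((0.465 − 0.74)/0.258) = Φ(−1.07) = 0.14. A one-sided rule needs only an estimate above −0.465: Φ((0.74 + 0.465)/0.258) = Φ(4.67), essentially 1.

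**Comparators side by side.**

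| Place | Comparator |
|---|---|
| Question 1 | usual practice and advanced dressing |
| Question 2 | usual practice |
| Definition of effective | usual practice |
| 3a, noninferiority | usual practice |
| 3i, trigger for 80% CIs | usual practice |
| 3i, rule for questions 1 and 2 | group 1 or group 3, both steps |

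**The case against.** The strongest reply is that the intent is plainly conventional. Sections 2 and 3a state a directional expectation, 3i speaks of attaining statistical superiority with 95% CIs, and safe and effective have their own definitions. A biostatistician reading all of this would hardly call an interval centred on zero superior. That stands, and it makes this most likely a drafting error. It does not remove the conflict between the two paragraphs of 3i.

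Four stronger readings are tempting and are not supported.

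- **That the trial plans an equivalence test.** The surrounding text aims at superiority; only the wording of the rule is an equivalence criterion.
- **That the direction is wrong whatever f is.** The appendix could define f as a region beyond a margin, or one open on the favourable side, and the rule would then work. The visible text does not say so, and one symbol for both sets of margins makes it harder to infer.
- **That the advanced dressing is a second route to success.** No sentence says that meeting either comparison suffices. The word or may simply mean that each comparison is reported, as question 1 requires. The risk is ambiguity, not a declared alternative.
- **That the error rates describe this trial.** They depend on an assumed symmetric f.

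It can also be objected that correcting the rule should not alter the noninferiority interval. That is right. With an assumed margin of 0.5 SD and no true difference, moving from an 80% to a 95% CI would cut power at 30 per arm from 0.74 to 0.49, and would raise the number needed for 80% power from 37 to 63 per group. That is a separate design choice, and nothing in this point argues for it.

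**Conclusion.** The point holds as a defect of the written rule. As worded, 3i tests containment for both superiority and noninferiority, against the plan's own directional aim, and its noninferiority comparators contradict 3a and the preceding paragraph of 3i. The comparator conflict does not depend on f. The direction problem depends on the visible text being complete, so an appendix that defined one-sided regions would reduce it to unclear wording.

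The size is illustrative: at 30 per arm and an assumed symmetric f of 0.8 SD, about 72% against 2.5% at no effect, and 4% against 80 to 81% at a true benefit of 0.74 SD. Other values of f change the figures. The pattern of passing at no effect and failing at large benefit remains for any symmetric f wide enough to be met with useful frequency. The rule should be corrected before analysis, because following it as written can give the wrong answer.

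**What to change.** Replace the rule for questions 1 and 2 in section 3i with the following.

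1. **Superiority:** the intention-to-treat 95% CI for group 2 minus group 1 lies wholly on the favourable side of zero. State for each outcome which direction is favourable.
2. **Noninferiority:** only the unfavourable bound of the plan's noninferiority CI must be better than the prespecified margin, with no limit on the favourable side. The 80% level and the removal of drop-outs stay as written; this point does not change them.
3. **Comparator:** both decisions are made against usual practice, as 3a and the preceding paragraph of 3i already have it.
4. **Group 3:** report the comparison that question 1 asks for as an estimate with its CI, not as an alternative way to succeed.
5. **Margins:** use separate symbols for any superiority and noninferiority margin, and point to where each is defined.

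Align question 1, question 2, the definition of effective, 3a and both paragraphs of 3i to this wording. The cost is a text amendment. Design, sample size and data collection do not change.

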Decrease in SCLU surface area will be used to answer research question 1. Conducting a power analysis for this study is challenging because only one study of SCLUs has demonstrated a statistically significant outcome, and the effect size was obscured by high standard deviations, which is a common problem in studies of wounds.⁸ Improvised plastic dressings similar to the study dressings were used in 49 chronic pressure ulcers in elderly patients, which are often slow to close, if they heal at all.⁶⁰ These two studies demonstrated a significant difference with confidence intervals of 99% with ~25 patients per group. Based upon these sample sizes and the Central Limit Theorem, it is reasonable to set the minimum sample size for this study at 30 patients per group,.^{88,89}

d. Variables

Dependent Variables (measured weekly - tools and permissions in appendices):

- 1. Persistent wound pain (using the Faces Pain Scale Revised (FPS-R))
- 2. Procedural (dressing change) wound pain
- 3. Amount of pain medication taken, including a total number of morphine equivalents plus non-opioid pain medications
- 4. Approximate time spent standing, or sitting with leg dependent without compression (estimated hours per week)
- 5. Patient overall quality of life (assessed with the ASCQ-Me Emotional, Pain, Social Functioning, Stiffness, and Sleep Impact Short Forms)
- 6. Patient wound-specific quality of life (assessed with the Wound QoL tool)
- 7. Materials costs (estimated, using lowest retail costs on Amazon.com for items not on the UWI price sheets)
- 8. Time spent performing dressing changes
- 9. Wound complication rates (e.g., wound infection, healing impairing maceration, wound deterioration)
- 10. Change in wound surface area (measured in cm² electronically using software that automatically corrects for skew, such as HealthEPix or WoundMatrix)⁹⁰

Dependent Variables (measured one time, at graduation from study)

- 11. Wound closure time, in weeks (see definitions; verified two weeks later. Omit patients whose wounds did not fully close they are included in 10., above.)
- 12. Acceptability of dressing choice patient (5 point Likert scale and qualitative free response)
- 13. Acceptability of dressing choice family member (5 point Likert scale and qualitative free response)
- 14. Acceptability of dressing choice UHWI staff (5 point Likert scale and qualitative free response)

Independent Variables (documented at initial study visit):

1. Patient gender

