- 2. Age of open wound prior to entrance into study (in weeks, patient/family report)
- 3. Previous ulcer treatments (if any)
- 4. Education level (in years)
- 5. Smoking or any use of nicotine (yes/no in past week)^{84,85}
- 6. Mid-arm circumference (a surrogate for nutritional status) 91,92
- 7. Initial area of SCLU in cm^2 (see methods for multiple adjacent SCLUs)
- 8. Initial depth of SCLU at deepest point, in cm
- 9. Anatomic location of SCLU
- 10. ASCQ-Me baseline scores (all measures see appendices)
- 11. Social isolation (lives alone, without nearby support)⁸⁶
- e. Inclusion and exclusion criteria

Inclusion Criteria:

- > Diagnosed with HbSS or HbS β^0 sickle cell disease
- > Ages 13 70 years at study initiation (able to comprehend and give consent)⁸²
- > Males and females, pregnancy is not an issue
- > Open wound below the knee, not including the plantar surface of the foot
- > Wound open for longer than one month (defined as a chronic SCLU)
- > Traumatic, spontaneous, or recurrent SCLU (all etiologies)

Exclusion Criteria:

- > Patient younger than 13 years of age at study initiation
- > Patient older than 70 years of age at study initiation
- Wound open for less than one month by conclusion of study enrollment period (acute wounds could be traumatic wounds unrelated to sickle cell diagnosis)
- ➤ Diagnosis of cancer, hypertension, or chronic renal failure⁸²
- ➤ Diabetes (will screen for undiagnosed diabetes)⁸²
- Active wound infection (evidenced by clinical signs of malodor, dark-colored or thick drainage, or significantly increased warmth at the periwound) which is not resolved by the conclusion of the study enrollment period
- Osteomyelitis (if osteomyelitis is suspected, an ESR will be drawn; > 70mm/h with high platelet levels and low serum albumin warrants a bone biopsy)^{93,94}

> Hydroxyurea use (may be a confound because it reduces inflammation and negates much of the pathology of SSD – may choose to abstain for the study)^{7,95}

f. Sampling

- i. All eligible participants who consent to the study will be included. Participants will be randomized into one of the three groups immediately after the initial cleansing/debridement of their SCLU by the nurse using an electronic random number generator (an app). Waiting until the study dressing is to be applied to generate the random number will provide allocation concealment.

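### The ANCOVA covariate set is not fixed: entering all 11 independent variables could cost precision, choosing among them later would undermine the confidence intervals, and baseline pain is not on the list

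*Combined protocol and SAP*

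**What the plan says.** Section 3i (Statistical analysis) refers to the covariates twice. The groups are to be compared on each of 14 dependent variables, "taking into account any confounding from the 11 independent variables". Research questions 1 and 2 are then to be answered by ANCOVA, "with respect to each of the dependent variables, controlling for relevant patient characteristics (the independent variables").

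The 11 variables are listed in section 3d: gender, ulcer age, previous treatments, education, nicotine use, mid-arm circumference, initial area, initial depth, location, baseline ASCQ-Me scores and social isolation. Three of them can need more than one model term: "Previous ulcer treatments (if any"), "Anatomic location of SCLU" and "ASCQ-Me baseline scores (all measures see appendices"). The ASCQ-Me outcome is "assessed with the ASCQ-Me Emotional, Pain, Social Functioning, Stiffness, and Sleep Impact Short Forms", which is five forms.

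Section 3h says that persistent pain is assessed at baseline with the Faces Pain Scale – Revised. That score is not one of the 11.

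**The concern.** The text can be read in two ways, and each has a cost.

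- **All 11 enter.** The parenthesis in the ANCOVA sentence points this way. The model then spends many degrees of freedom in a trial planned at about 30 patients per group. Terms that do not predict the outcome widen the interval for the treatment difference.
- **A subset enters.** Limiting adjustment to relevant characteristics, or to any confounding found, suggests a choice made later. Under randomisation, baseline imbalance arises by chance. Choosing covariates by observed imbalance, by significance or by the resulting treatment effect means that the nominal 95% and 80% intervals no longer have their stated properties. Eleven variables allow 2¹¹ = 2,048 subsets for each outcome. Section 5 says that the research team cannot be blinded, and section 4 discloses that one of the researchers is employed by the maker of a study dressing, so a list fixed in advance also protects the trial's credibility.

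The list also leaves out the baseline measure closest to the pain outcomes. Persistent pain would be adjusted for education or arm circumference but not for its own starting value.

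**Working it through.** **The plan's own figure.** Section 3f plans 90 evaluable patients and allows for 25% dropout: 90 / (1 − 0.25) = 120. This reproduces the recruitment ceiling. The 30 per group cannot be derived, because no effect size, SD or power is given.

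**Number of terms.** One per variable gives 11. Five ASCQ-Me forms instead of one add 4, making 15 (assumption: the same five forms at baseline). Four categories each for location and previous treatments use 3 terms each, adding 2 + 2, making 19 (assumption: the section 3d list gives no categories).

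**Patients.** The cases are 90 (three arms, after dropout), 60 (two arms, after dropout) and 120 (three arms, if every recruit contributes to the intent-to-treat analysis).

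**Formulas.** Let ν = N − arms and p = covariate terms. Under randomisation, the expected ratio of adjusted to unadjusted variance of the treatment difference is

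(1 − R²) × (ν − 1) / (ν − p − 1),

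where R² is the share of within-arm outcome variance that the covariates jointly explain. The ratio equals 1 at R² = p / (ν − 1).

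| Model | p | Variance ratio at R² = 0 | SE ratio | Break-even R² |
|---|---|---|---|---|
| 90, three arms | 11 | 86/75 = 1.147 | 1.071 | 11/86 = 0.128 |
| 90, three arms | 19 | 86/67 = 1.284 | 1.133 | 19/86 = 0.221 |
| 60, two arms | 11 | 57/46 = 1.239 | 1.113 | 11/57 = 0.193 |
| 60, two arms | 19 | 57/38 = 1.500 | 1.225 | 19/57 = 0.333 |
| 120, three arms | 11 | 116/105 = 1.105 | 1.051 | 11/116 = 0.095 |
| 120, three arms | 19 | 116/97 = 1.196 | 1.094 | 19/116 = 0.164 |

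A simulation of the 60- and 90-patient settings (2,500 runs each) agreed with the formula within simulation error. For example, 60 patients with 19 uninformative terms gave 1.511 against 1.500.

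**In terms of power.** With 30 per arm, 80% power at two-sided 0.05 corresponds to a difference of about 0.72 SD. This is a reference value, not one from the plan. Uninformative terms cut the effective size to between 30/1.500 = 20.0 and 30/1.147 = 26.2 per arm, and power to between 63% and 74%.

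**When the covariates are informative.** At R² = 0.5 the ratio is 0.57 to 0.75 across the four settings with 60 or 90 patients, so full adjustment would gain precision.

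**A three-term list by the same formula.** At R² = 0 the ratios are 86/83 = 1.036, 57/54 = 1.056 and 116/113 = 1.027.

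**The case against.** Several points on the other side stand.

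- **All 11 is a reading.** A reader might infer that every variable is certain to enter. The plan does not say so, and its wording leaves room for a subset. What is established is that no set is fixed. Some appendices are not in the public file, but the analysis section does not point to one for a covariate list.
- **Uninformative covariates are an extreme case.** Section 1b cites studies in other wound types that link ulcer duration, smoking, living alone and male sex to slower healing. Initial area may itself supply much of the break-even R² for the area outcome. Equally, section 1a says the determinants of healing in these ulcers are poorly understood, and the documents give no prognostic strength for any covariate, so neither extreme can be assumed.
- **Adjustment fixed in advance does not bias.** In a randomised trial, too many prespecified covariates cost precision only. The planned t tests and ANOVA do not bear this cost, although ANCOVA is the method named for questions 1 and 2.
- **Smaller samples have no source.** A reader might apply the 25% dropout to the 30 per group and infer much larger losses in the noninferiority step. The 30 is already the number after dropout. Recruitment could fall short, since 120 is a ceiling and enrolment closes after 60 days, but no lower figure is given. Closure time is analysed in closers only, so its sample is smaller, but no closure rate is given from which to size the effect.
- **Scale is not stated.** A reader might infer that ulcer age and area enter untransformed. Section 3d gives recording units only.
- **A short list is partly judgement.** Section 1a reports no relation between ulcer size and pain, so area may add little to the pain models. For 60 patients, going from two terms to three changes the ratio at R² = 0 only from 57/55 = 1.036 to 57/54 = 1.056.

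**Conclusion.** The concern holds in this form: the adjustment set and its coding are not fixed, and the listed variables omit baseline Faces Pain Scale pain.

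If all 11 enter, variance rises by at most about 15% to 28% (90 patients, three arms), 24% to 50% (60 patients, two arms) or 10% to 20% (120 patients). The lower figures need no coding assumption beyond one term per variable; the upper ones rest on the assumed 19 terms. Covariates with a joint R² above 0.13 to 0.33 in 60 to 90 patients would repay their cost. Only the top of that range, 19 terms in 60 patients, calls for strong prognostic value.

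If covariates are chosen from the data, the harm is to the reliability of the intervals. The documents do not allow that harm to be sized.

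The pain omission is clearest for persistent pain. The ASCQ-Me Pain form, assumed to be among the baseline scores, is a different instrument. For procedural pain, section 3h names no separate baseline, so baseline persistent pain is the nearest available measure.

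**What to change.** Before analysis, replace the two adjustment statements in section 3i with one list for every ANCOVA:

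1. the baseline value of the outcome where it is collected, including baseline Faces Pain Scale pain for the pain outcomes;
2. initial ulcer area;
3. ulcer age at entry.

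A log scale is suggested for area and age because both are likely to be skewed. For the area outcome, items 1 and 2 coincide. State that no covariate is added or dropped because of baseline imbalance or significance. Report the remaining variables in the baseline table and in one labelled sensitivity analysis, with the categories for location and previous treatments written down beforehand.

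The cost is plan wording only; no new data are needed. The downside is that a chance imbalance in an unlisted variable is handled only in the sensitivity analysis.
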